# 10.2.4. Comprehensive Follow-up at Scheduled Study Visits Following Premature Discontinuation of Study Drug

It is important to note that subjects who discontinue study drug early will be required, wherever possible, to continue with scheduled visits for the duration of the study. Data collection required for subjects who discontinue study drug early will be comprehensive (as described in the Time and Events Schedule) and will be essential for every randomized subject. Subjects will continue to be followed up for specific data collection, including, vital signs, body weight, laboratory assessments, serious adverse events, adverse events of interest, and adverse events of special interest for the duration of the study. For subjects who prematurely discontinue study drug, sites will be required to make a final contact (eg, schedule the last follow-up visit) at what would have been their final scheduled visit.

#### **Alternate Follow-up Methods**

If a subject who discontinued study drug prior to Week 52 refuses or is unable to return for their regularly scheduled visits, he/she will be asked to return at a reduced visit schedule including key visits (ie, Weeks 12, 26, 42, and 52). If the subject refuses or is unable to return to the clinic for follow-up visits, the subject can be contacted at Weeks 12, 26, 42, and 52 to obtain adverse

events, and prior/concomitant medications. At the very minimum, attempts should be made at Week 52 to obtain adverse events and prior/concomitant medications. These alternate follow-up methods should be planned to coincide with the visit times outlined in the Time and Events Schedule. Details regarding discussions via telephone, email, or other such contacts must be properly documented in source records, including responses by the subject.

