It should be noted that if the subject does not meet HbA1c rescue criterion (either at scheduled or unscheduled visit), the subject may be still rescued if it is the investigator's opinion, based on recent SBMGs/FPG values, that the subject's glycemic control is progressively deteriorating and unlikely to improve with reinforcement of compliance with background AHA therapy and diet and exercise counseling. If a subject has scheduling conflicts and cannot attend an unscheduled visit at the site to assess the HbA1c criterion, the site may instruct the subject to obtain an HbA1c assessment at a local laboratory.

**Table 2:** Glycemic Rescue Criteria

Baseline HbA 1c	HbA 1c change from baseline
<9.0%	>0.8%
≥9.0%	>0.5%

Key: HbA1c=glycated hemoglobin

Any subject that qualifies for initiation of rescue therapy should return to the investigational site, per the investigator's judgment, after an overnight fast, for measurement of HbA1c, FPG, and serum chemistry.

If new rescue therapy is initiated, it will be supplied locally by the sponsor or reimbursed by the sponsor as appropriate. Investigators must complete the appropriate eCRF (documenting initiation of therapy) for subjects starting on rescue medication.

For subjects rescued based on SMBG and/or FPG instead of HbA1c, the most recent values supporting such decision will be documented into the appropriate eCRF.

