# 11.2. Sample Size Determination

The primary hypothesis of the study is that canagliflozin is superior to placebo in glycemic control, as measured by the change from baseline to Week 26 in HbA1c.

The sample size calculation is based on the 2-stage randomization design using a 2-sample, 2-sided t-test with Type 1 error rate of 0.05. Based on the following assumptions on treatment effect (0.4% to 0.5%) and an associated common standard deviation of 0.9% and assuming 50% of the subjects will meet the re-randomization criteria at Week 12, it is estimated that at least 66 subjects per group will be required to achieve approximately 85% power. To account for attrition due to study discontinuation in a longitudinal analysis (to be described below), a 10% sample size inflation factor is employed (Lu 2008), and a total of at least 146 subjects (73 per arm) will be randomized in this study.

Treatment group	Meeting re- randomization criteria at Week 12	Placebo-subtracted group difference in change in HbA 1c from baseline to Week 26
canagliflozin 100 mg to canagliflozin 100 mg	No	0.5%
canagliflozin 100 mg to canagliflozin 100 mg	Yes	0.4%
canagliflozin 100 mg to canagliflozin 300 mg	Yes	0.5%

For subjects who are on background metformin (with or without insulin), it is estimated that at least 33 subjects per group (after accounting for attrition due to study discontinuation) will be required to achieve approximately 85% power to assess the efficacy of canagliflozin on a background of metformin.

Treatment group (add-on to metformin)	Meeting re- randomization criteria at Week 12	Placebo-subtracted group difference in change in HbA 1c from baseline to Week 26
canagliflozin 100 mg to canagliflozin 100 mg	No	0.75%
canagliflozin 100 mg to canagliflozin 100 mg	Yes	0.65%
canagliflozin 100 mg to canagliflozin 300 mg	Yes	0.75%

The assumed treatment effect above is based on a subgroup analysis of subjects with baseline eGFR of  $\geq$ 90 mL/min/1.73m^2 from the add-on to metformin study of canagliflozin in adults (ie, Study DIA3006).

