#### **Post-Randomization:**

- All subjects should return for scheduled in-clinic visits when possible. As a reminder, the double-blind treatment phase provides a +/-7 day window around each visit for scheduling.
- For subjects who are unable to return to complete a scheduled in-clinic visit, the scheduled inclinic visit should be changed to a virtual contact (eg, via telephone, video-conferencing, or other channels) to collect information on the subject's current health status, medication compliance, and any new or ongoing AEs as well as changes in concomitant medications. The virtual method used for contacting the subject must be allowable per local regulations and documented in the subject's source record as well as entered in the Comments eCRF clearly designating the contact as "COVID-19-related". Additional virtual contacts may be conducted in between scheduled visits if deemed clinically appropriate by the Investigator and all virtual contacts must be recorded as outlined above.
- All subjects should continue to have protocol-specified central laboratory assessments when possible. If central laboratory tests cannot be performed or ambient samples cannot be collected by courier due to local restrictions and regulations relating to the COVID-19 outbreak, the use of an accredited local laboratory is permitted for all visits and all protocol-specified laboratory assessments, especially those outlined for Weeks 12, 26, and 52 and for essential laboratory measurements related to safety/efficacy (eg, HbA1c, eGFR, etc) as outlined in the Protocol's Time and Events Schedule. Additional guidance on the recording of local laboratory assessments in the clinical database can be found in the eCRF Completion Guidelines. Site Managers must be informed of all local laboratory assessments performed.

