5.2.3. Analysis Methods

Primary Analysis

The primary analysis is based on the FAS dataset, including all HbA1c measurements collected from randomization to Week 26, including the measurements collected after treatment discontinuation or initiation of rescue medication.

The primary analysis will be based on pattern mixture model (PMM), as described below:

- Any intermediate missing data will be multiply imputed using Monte Carlo Markov Chains (MCMC), under a Missing at Random (MAR) assumption.
- Then the participants with ICEs and missing Week 26 HbA1c values will be multiply imputed using a multiple imputation (MI) model based on the participants with ICEs and non-missing Week 26 HbA1c values. An MI regression will be applied to impute all monotone missing values, using treatment group, stratification factors, baseline HbA1c and the change from baseline in HbA1c at Weeks 6, 12 and 20. If this MI model does not converge then a Copy Reference MI model will be used instead, as described in the sensitivity analysis section.
- Any Week 26 missing values for change from baseline in HbA_{1c} in participants without ICEs will be imputed based on the MI regression (see description above) applied to all participants.
- A total of 1000 multiple imputations will be performed. A seed equal to 345 will be used in all MI models.
- After MI, each of the multiply imputed datasets will be analyzed using analysis of covariance (ANCOVA) with terms for treatment, stratification factors, and baseline HbA_{1c}.
- Rubin's rules will be applied to combine the ANCOVA results across the imputed datasets, including the Week 26 LS Means for each treatment group and the difference vs placebo in LS Means.

Secondary analysis of the primary efficacy endpoint

The secondary analysis is based on a subset of subjects on background metformin (with or without insulin) from the FAS dataset, including all HbA1c measurements collected from randomization to Week 26, including the measurements collected after treatment discontinuation or initiation of

rescue medication. The attributes of estimand for this analysis is the same as the primary efficacy estimand except the population is a subset of subjects with background metformin (with or without insulin). The same analysis based on PMM will be performed as described above.

Bayesian analysis of the primary efficacy endpoint

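### Subjects who stop drug before Week 26 and decline all clinic visits are not asked for a Week 26 HbA1c, so their primary treatment-policy value must be imputed from what may be few donors

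*Protocol*

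**What the plan says.** Protocol Section 10.2.4 sets out follow-up after early discontinuation of study drug in descending steps:

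1. All scheduled visits, with laboratory assessments.
2. If the subject refuses or cannot attend these, a reduced clinic schedule at Weeks 12, 26, 42 and 52.
3. If the subject refuses or cannot come to the clinic, a contact at those same weeks for adverse events and medications.
4. A floor: "At the very minimum, attempts should be made at Week 52 to obtain adverse events and prior/concomitant medications".

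HbA1c is on the Time and Events Schedule at Week 26, so steps 1 and 2 collect it. Steps 3 and 4 do not. Section 10.3.2 is similar: for subjects who stop drug but agree to follow-up, it names a Week 52 visit and does not mention Week 26. Section 10.2.2 requires an end-of-treatment visit, which includes HbA1c, when drug is stopped, but lets it be omitted if the subject cannot be seen within 30 days.

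The primary estimand (Protocol 11.3.1, SAP 5.2.2) uses Week 26 HbA1c whether or not the subject has discontinued treatment or started rescue. Under SAP 5.2.3, a missing Week 26 value after either event is imputed from a model "based on the participants with ICEs and non-missing Week 26 HbA1c values". If that model does not converge, Copy Reference imputation replaces it.

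A local-laboratory HbA1c is accepted in two other places. Protocol 6.2.2 allows it for the rescue assessment: "If a subject has scheduling conflicts and cannot attend an unscheduled visit at the site". Under COVID-19 restrictions, "the use of an accredited local laboratory is permitted for all visits and all protocol-specified laboratory assessments".

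**The concern.** A treatment-policy estimand depends on outcomes measured after the intercurrent event. The subjects whose values are hardest to predict are those who stopped drug and withdrew from clinic visits, and for them the plan does not request the primary measurement at the primary time point. The floor points to Week 52 and to safety data.

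Each such missing value has two effects. It has to be imputed, and the subject is absent from the set on which the imputation model is fitted. The donors are subjects with an intercurrent event who did supply a Week 26 value, and they may differ from those who declined. Rescued donors stay on blinded study drug (Protocol 6.2.2), so they are not a close match for subjects who stopped it. At stake are some precision and, more importantly, reliance on an untestable assumption in the primary analysis. The metformin-background test uses the same method on a smaller group.

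**Working it through.** **Reproducing the plan's sample size.** Protocol 11.2 uses a "2-sample, 2-sided t-test with Type 1 error rate of 0.05", SD 0.9%, and effects of 0.5%, 0.4% and 0.5% for the three dose paths, "assuming 50% of the subjects will meet the re-randomization criteria at Week 12".

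- Mean effect = 0.50 × 0.5 + 0.25 × 0.4 + 0.25 × 0.5 = 0.475%.
- The normal approximation gives 65 per arm. The exact noncentral t gives 66, with power 85.3%. The plan states that "at least 66 subjects per group will be required to achieve approximately 85% power", so its figure is reproduced.
- Inflation: 66 × 1.10 = 72.6, rounded up to 73 per arm, 146 in total.
- With all 73 per arm observed, power is 88.6% (exact t).

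**Loss of Week 26 values in general.** The documents give no expected share missing, so the share is an assumption, shown as a range. The third column keeps the effect at 0.475% and drops subjects at random. The fourth gives the missing canagliflozin subjects a placebo-like mean, so the effect becomes 0.475 × (1 − k/73), with the standard error of 73 per arm.

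| Share missing | k per arm | Dropped at random | Placebo-like mean |
|---|---|---|---|
| 5% | 4 | 86.8% | 84.9% |
| 10% | 7 | 85.3% | 81.7% |
| 15% | 11 | 83.0% | 76.7% |
| 20% | 15 | 80.5% | 71.1% |

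A random loss of 10% returns the planned power.

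**Imputing from a donor set.** Let f be the share of each arm with an intercurrent event of either kind, and q the share of those who lack Week 26 HbA1c. Donors per arm = 73 × f × (1 − q). If missing values are estimated from donors in the same arm, the variance of the arm mean is inflated by about V = (1 − f) + f/(1 − q). Power is then taken at an effective 73/V per arm, with effect 0.475% and SD 0.9% (normal approximation).

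| f | q | Donors per arm | V | Power |
|---|---|---|---|---|
| 10% | 0 | 7.3 | 1.00 | 89.0% |
| 10% | 50% | 3.7 | 1.10 | 86.0% |
| 10% | 75% | 1.8 | 1.30 | 79.9% |
| 20% | 50% | 7.3 | 1.20 | 82.9% |
| 20% | 75% | 3.7 | 1.60 | 71.3% |

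Example: for f = 20% and q = 75%, V = 0.80 + 0.20/0.25 = 1.60 and 73/1.60 = 45.6 per arm, giving 71.3%. If half of those missing values were retrieved, q = 37.5%, V = 0.80 + 0.20/0.625 = 1.12 and 73/1.12 = 65.2 per arm, giving about 85%.

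**Metformin subset.** With 33 per group, f = 10% and q = 50%, donors are 33 × 0.10 × 0.50 = 1.65 per group, or about 3 in total.

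The V formula ignores covariates and any sharing across arms, so it is a guide to order of size only. It also holds the effect at its planned value. And q covers every reason for a missing value, including withdrawn consent and loss to follow-up, which Section 10.2.4 cannot recover. The table therefore bounds the problem and does not estimate what the fix would gain.

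**The case against.** The best defence is that the floor is a last resort and not the plan. Section 10.2.4 first requires the full schedule, and then asks subjects who cannot keep it back to the clinic at Week 26. A reader who sees only the floor might infer that HbA1c is not sought at all after discontinuation. The documents do not support that: it is sought on the full schedule, on the reduced schedule and at the end-of-treatment visit.

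Nor is the endpoint simply lost. Subjects who stop after their Week 26 visit are unaffected. An end-of-treatment HbA1c taken on Days 163 to 211 falls in the Week 26 window (SAP Table 1), and an earlier one can inform the imputation. Values still missing are imputed, with Copy Reference and tipping-point sensitivity analyses. This stands, with one limit. Protocol 3.2 says HbA1c takes about 12 to 16 weeks to settle after a change in control, so a value taken at stopping mainly reflects control on drug.

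A reader might also infer that a few retrieved values would decide whether the primary model can be fitted. With main effects, the imputation regression has about 10 coefficients: intercept, treatment, three for background therapy, one for age group, baseline and three earlier changes. Under f = 10% and q = 50% there are about 7 donors over both arms. But rescued subjects are donors too, no rescue rate is given, and the 10% in Protocol 11.2 is a sample-size allowance for study discontinuation, not a forecast of intercurrent events. Failure to fit is not shown, and the SAP provides for non-convergence.

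Finally, the target group has already declined a Week 26 clinic visit, so a local sample may also be declined. That stands as a limit on the yield.

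**Conclusion.** The point holds for a defined subgroup: subjects who stop study drug before Week 26, stay in the study, and decline both the regular and the reduced clinic schedule. No Week 26 HbA1c is requested from them, which is out of line with the treatment-policy estimand and with an imputation model that needs observed values after the intercurrent event. The size of this subgroup is not given and may be small. Across the assumed range, power runs from about 86% (10% with an event, half of them missing) to about 71% (20%, three quarters missing). At the low end the cost to power is slight, and the gain is mainly less dependence on an untestable assumption. The change is worth making, but the gap does not by itself undermine the primary analysis.

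**What to change.** In Protocol 10.2.4, insert a step between the reduced clinic schedule and the contact. For a subject who stopped drug before Week 26 and declines clinic visits, request one HbA1c within the SAP's Week 26 window (Days 163 to 211), at a local laboratory if needed. Name Week 26 HbA1c as the priority item for these subjects, and keep the Week 52 safety contact as the last step. Align Section 10.3.2 with this.

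Section 5 masks HbA1c after Day 1 except at Week 12 and once rescue has started. A local result should therefore go to the database without being shown to the site, by an arrangement consistent with the existing threshold alert in Section 6.2.2.

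The cost is protocol wording, site instruction and the masking arrangement. No subjects and no new type of assessment are added. The downsides are some local-assay values in the primary endpoint, which should be flagged in the data, and an uncertain yield among subjects who have already declined visits.

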# 10.3. Withdrawal from the Study

A subject will be withdrawn from the study for any of the following reasons:

- Death
- Lost to follow-up
- Withdrawal of consent or assent (either by the subject and/or the parents[s]/legal guardian[s])

For subjects (and/or parents[s]/legal guardian[s]) withdrawing from the study before study completion, an early withdrawal evaluation should be performed as soon as possible after the last dose of study drug is taken. Refer to the Time and Events Schedule for procedures to be conducted at the EOT/early withdrawal evaluation.

# 10.3.1. Lost to Follow-up

If a subject is lost to follow-up, all reasonable efforts must be made by the study-site personnel to contact the subject and/or parent(s)/legal guardian(s) and to determine the subject's status and the reason for discontinuation/withdrawal. This should include repeated telephone calls, certified letters, email requests, etc. To ensure access to follow-up subjects, the study sites should attempt to obtain both primary and secondary telephone contact numbers (eg, home, work, and mobile phone numbers), as well as other contact information (eg, email addresses) from subjects before randomization. In addition, the study site should emphasize the importance of follow-up information to the subject before randomization. The measures taken to obtain follow-up information must be documented. Third-party vendors may be used to locate subjects lost to follow-up where permitted by local laws and regulations.

Subject and/or parent(s)/legal guardian(s) will be asked as a condition of entry into the study to agree to grant permission for the investigator to consult family members, the subject's physicians and medical records, or public records, to determine the subject's status during the study, in the event the subject is not reachable by conventional means (eg, office visit, telephone, email, or certified mail). The subject and/or parent(s)/legal guardian(s) are also to be advised that if the study site of the study doctor closes, and the study doctor cannot reach the subject to inform him/her, the contact information may be transferred to another study site where a new study doctor will consult with family members, the subject's physicians and medical records, or public records to determine the subject's status during the study.

#### 10.3.2. Withdrawal of Consent

Withdrawal of consent (either by the subject or the parents[s]/legal guardian[s]) should be a very unusual occurrence in a clinical trial. The investigator should make every effort to maintain a

good relationship with subjects and their parents[s]/legal guardian[s] to avoid this occurrence. Unless consent is specifically withdrawn, subjects are expected to be followed up through the end of the study.

Subjects and/or parents[s]/legal guardian[s] who request to withdraw consent from the study should be asked if they are agreeable to be contacted to obtain post-treatment follow-up information, including the Week 52 post-treatment follow-up visit. Subjects and/or parents[s]/legal guardian[s] who are not agreeable to follow-up will be withdrawn from the study as "withdrawal of consent" and will not be scheduled for the Week 52 post-treatment follow-up visit. Subjects and/or parents[s]/legal guardian[s] who wish to discontinue study drug but agree to further follow-up have, by definition, not withdrawn consent to the trial and will be scheduled to return to the clinic for the Week 52 post-treatment follow-up visit (see Section 10.2, Study Drug Treatment Premature Discontinuation, Reinstitution, and Follow-up). The recording of withdrawal of consent in the eCRF for this study will occur after a discussion between the investigator and the subject along with the parents[s]/legal guardian[s] has taken place.

For subjects and/or parents[s]/legal guardian[s] requesting to withdraw consent, it is recommended that the withdrawal is in writing. If the subject and/or parents[s]/legal guardian[s] refuses or is physically unavailable, the study site should document and sign the reason for the subject's and/or parents[s]/legal guardian[s] failure to provide a request to withdraw and maintain this documentation in the subject's source records.

When a subject and/or parents[s]/legal guardian[s] withdraws consent before completing the study, the reason for withdrawal of consent is to be documented in the eCRF and in the source document. Study drug assigned to the withdrawn subject may not be assigned to another subject. Subjects who withdraw consent (either per their own decision and/or by the parents[s]/legal guardian[s]) will not be replaced.

If a subject and/or parents[s]/legal guardian[s] had previously withdrawn consent but decides to retract that withdrawal, the subject and/or parents[s]/legal guardian[s] will be re-consented. The investigator will be responsible for making all required notifications to the Institutional Review Board (IRB) or Independent Ethics Committee (IEC).

# 10.4. Withdrawal from the Use of Samples in Future Research

A subject who withdraws consent from the study will have the following options regarding the optional research samples:

- The collected samples will be retained and used in accordance with the subject's original separate informed consent for optional research samples.
- The subject may withdraw consent for optional research samples, in which case the samples will be destroyed and no further testing will take place. To initiate the sample destruction process, the investigator must notify the sponsor study site contact of withdrawal of consent for the optional research samples and to request sample destruction. The sponsor study site contact will, in turn, contact the biomarker representative to execute sample destruction. If

requested, the investigator will receive written confirmation from the sponsor that the samples [has] [have] been destroyed.

